5.8.1 Missing data for efficacy and safety endpoints

Missing data for each efficacy endpoint will be handled as described in Sections 8.2, 8.3, 8.4 and 8.6.

For continuous endpoints, change from baseline will be set to missing at visits with missing post-baseline values or where data were imputed to missing. Continuous efficacy endpoints will be set to missing for subjects who received rescue treatment before Week 12.

For binary endpoints, subjects with missing efficacy data, early withdrawals, or subjects who received rescue treatment before Week 12 will be imputed as non-responders and therefore treated as a failure (e.g., no ACR20/50/70 response, DAS28-CRP remission or no moderate/good EULAR response).

Additional rules for handling of missing data and rescue treatments are detailed below:

- *Missing efficacy data.* Visits with missing data (due to a missed visit or missing component of a composite endpoint) will be set to treatment failure.
- *Early withdrawals.* Only visits following the early withdrawal visit will be set to treatment failure.
- *Prednisone equivalent >10 mg/day.* The visit after a period (time from previous visit up to the day before the current visit) of average daily corticosteroid use exceeding 10 mg/day prednisone will be set to treatment failure and continuous endpoints set to missing due to rescue.
- *Corticosteroid injection.* If subject received a corticosteroid injection within 30 days prior to a study visit, that visit will be set to treatment failure and continuous endpoints set to missing due to rescue.
- *b/ts/csDMARD.* Subjects who receive treatment before Week 12 with biologic, targeted synthetic, or additional conventional synthetic DMARD, or increased dose of background

conventional synthetic DMARD will be set to treatment failure at all subsequent visits and continuous endpoints set to missing due to rescue.

- *Missing baseline value.* For efficacy endpoints, a missing value at baseline will not be imputed, and the endpoint will be set to missing for all visits.
- *Missing analytes/ retests.* If an analyte value is missing/its concentration cannot be reliably determined (e.g., sample was lost, damaged, etc.), a retest value will be used for that analyte. If an initial value is non-missing and reliable but the analyte was retested, the value that coincides with the date of clinical assessment will be used. If neither an initial nor retest value is available, the analyte value will be set to missing.

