- The primary ACR20 response at Week 12 will be analyzed with the Cochran-Mantel-Haenszel (CMH) test. For Stage 1 subjects, stratification factors are prior inadequate response or loss of response to JAKi and RA disease severity of < 4 TJC28 or < 4 SJC28 at Day 0. For Stage 2 subjects, stratification factors are RA disease severity at Day 0 and inadequate response or loss of response to ≥ 4 biological DMARDs with ≥ 2 mechanisms of action. Other binary response endpoints at Week 12 will be analyzed similarly.
- The secondary efficacy endpoints that are continuous variables (change from baseline) will be analyzed using Mixed-effect Model Repeated Measure (MMRM) statistics. The repeated-measures analysis will be based on the restricted maximum likelihood method assuming an unstructured covariance structure to model the within-subject errors. The model, including:

treatment group; stratification factors - inadequate response or loss of response to JAKi and RA disease severity at Day 0 (Stage 1 subjects); RA disease severity at Day 0 and inadequate response or loss of response to ≥ 4 biological DMARDs with ≥ 2 mechanisms of action (Stage 2 subjects); visit (all visits from Week 4 to Week 12); and treatment-by-visit interaction as fixed effects and baseline as a covariate, will be used to test the difference between the treatment and control group in a given efficacy endpoint change from baseline to Week 12. The data collected after receiving rescue therapy will be set to missing. Therefore, the MMRM analysis assumes a missing-at-random (MAR) mechanism for missing data due to dropout and post-rescue data.

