8.3.3 Primary Analysis

The primary analysis of the ITT population will be the CMH test. ACR20 response is the outcome variable. Subjects who received rescue treatment before Week 12 or who had missing data at Week 12 will be considered non-responders in the primary analysis.

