8.4.1 Definitions of key secondary endpoints

ACR20 response at Week 12 from Day 0

A subject achieves ACR20 response when this subject experiences a \geq 20% improvement at Week 12 from the post-surgical baseline at Day 0 in TJC28 and SJC28 and 3 out of 5 ACR core measures and follows the same general and statistical analyses as for ACR20 response at Week 12 from baseline on the day of informed consent (see Section 8.3.1).

DAS28-CRP good/moderate EULAR response at Week 12

DAS28-CRP EULAR response at Week 12 is defined based on the combination of the current DAS28-CRP score and its improvement relative to baseline on the day of inform consent as illustrated in **Table 7**.

Table 7: EULAR Response Criteria

DAS28-CRP Score Week 12	DAS28-CRP Score Decrease from Baseline Value		
	> 1.2	> 0.6 to ≤ 1.2	≤ 0.6
≤ 3.2	Good response	Moderate response	No response
> 3.2 to ≤ 5.1	Moderate response	Moderate response	No response
> 5.1	Moderate response	No response	No response

A subject is considered having a moderate treatment response at Week 12 if:

- DAS28-CRP score improvement from baseline to Week 12 is > 0.6 and ≤ 1.2 , and the DAS28-CRP score at Week 12 is ≤ 5.1 ; or
- DAS28-CRP score improvement from baseline to Week 12 is > 1.2 , and the DAS28-CRP score at Week 12 is > 3.2 .

A subject is considered having a good treatment response at Week 12 if:

- DAS28-CRP score improvement from baseline to Week 12 is > 1.2 and the DAS28-CRP score at Week 12 is ≤ 3.2 .

If the post-baseline DAS28-CRP score is missing, then the corresponding EULAR category will be missing.

Missing DAS28-CRP values will be considered as not achieving remission.

DAS28-CRP response (MCID -1.2) at Week 12

A DAS28-CRP score reduction by at least 1.2 from baseline on the day of inform consent to Week 12 represents the MCID response (see Section 8.6.1).

HAQ-DI response (MCID -0.22) at Week 12

A HAQ-DI score reduction by at least 0.22 from baseline on the day of inform consent to Week 12 represents the MCID response (see Section 8.2.5).

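### SAP 5.8.1's visit-level steroid bullets contradict the rule that rescue before Week 12 is non-response, for subjects whose only rescue is early steroid use

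*SAP*

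**What the plan says.** **Subject-level rule.** Protocol 17.7, with Sections 3 and 14.5, imputes non-response for the primary and key secondary endpoints in any subject who starts rescue before Week 12. Section 17.7 names ACR20, EULAR, DAS28-CRP and HAQ-DI response. SAP 8.3.3 agrees for the primary analysis: "Subjects who received rescue treatment before Week 12 or who had missing data at Week 12 will be considered non-responders in the primary analysis". So does the general sentence for binary endpoints in SAP 5.8.1: "subjects who received rescue treatment before Week 12 will be imputed as non-responders and therefore treated as a failure".

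**Visit-level rule.** The list that follows in 5.8.1 treats types of rescue differently.
- Injection: "If subject received a corticosteroid injection within 30 days prior to a study visit, that visit will be set to treatment failure".
- Oral steroid: the visit that closes a period "of average daily corticosteroid use exceeding 10 mg/day prednisone will be set to treatment failure".
- DMARD: a subject given a new DMARD, or more of the background "conventional synthetic DMARD will be set to treatment failure at all subsequent visits".

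**Precedence.** Section 5.8.1 opens with "Missing data for each efficacy endpoint will be handled as described in Sections 8.2, 8.3, 8.4 and 8.6". That covers missing data and does not mention rescue. ACR20 from Day 0 "follows the same general and statistical analyses as for ACR20 response at Week 12 from baseline on the day of informed consent" (SAP 8.4.1). Sections 8.4 and 8.5 give no separate main-analysis rescue rule for the other three key secondary endpoints.

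**What counts as rescue.** Protocol 3 and 14.5 include an injection within 30 days of any study visit and average oral use above 10 mg prednisone per day between any two study visits.

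**The concern.** A subject can be a Week 12 non-responder under one sentence of 5.8.1 and be left unfailed at Week 12 under a bullet a few lines below. The DMARD bullet carries failure forward and the steroid bullets do not, so a programmer could reasonably take the difference as intended and use the observed Week 12 response. That would credit a response after prohibited steroid use, contrary to the Protocol.

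Three of the exposed endpoints are key secondaries that support claims under the Hochberg procedure. If the choice is left until treatment assignments are known, a confirmatory result could rest on a reading picked afterwards.

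**Working it through.** **1. Who is affected.** Week 12 is nominally Day 84, Week 8 is Day 56 and Week 4 is Day 28 (schedule of assessments).
- Injection: 84 - 30 = Day 54, so injections on Days 0-53 fall outside the Week 12 look-back. All are still Protocol-defined rescue: Days 0-28 lie within 28 days of Week 4, and Days 29-53 within 56 - 29 = 27 days of Week 8.
- Oral: the period judged at Week 12 starts at Week 8, so excess use confined to intervals ending by Week 8 leaves Week 12 untouched.
- These spans are 54/84 = 64% and 56/84 = 67% of the blinded period.
- DMARD rescue, and steroid use inside the look-back, give the same Week 12 result under both rules.

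**2. One case.** An injection on Day 20 is 8 days before Week 4. The bullet fails Week 4 and says nothing about Week 12. Protocol 17.7, SAP 8.3.3 and the general sentence make Week 12 a non-response.

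**3. Endpoint by endpoint.**

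| Endpoint | SAP rescue rule, main analysis | Protocol 17.7 |
|---|---|---|
| ACR20 from consent | 8.3.3: non-response; 5.8.1: both readings | non-response |
| ACR20 from Day 0 | follows the primary (8.4.1); 5.8.1: both readings | non-response |
| EULAR good/moderate | 5.8.1 only: both readings; general sentence names it | non-response |
| DAS28-CRP MCID | 5.8.1 only: both readings | non-response |
| HAQ-DI MCID | 5.8.1 only: both readings | non-response |

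**4. Reproducing the stated power.** Inputs (SAP 3.4, 4.2.1, 8.3.2): 125 per arm, one-sided alpha 0.025, stop if the Stage 1 difference (30 per arm) is below 10 points. Exact two-stage binomial calculation with a pooled chi-square test:
- 50% versus 30%: 0.774 (SAP 0.773)
- 45% versus 30%: 0.555 (SAP 0.555)

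**5. Size, for primary ACR20 only.** Let f be the share of each arm affected, with those subjects responding at the arm's rate p. The subject-level response rate is p × (1 - f). The documents give no f, so 2% and 5% are assumptions. At 50/30:
- f = 2%: 49.0 - 29.4 = 19.6 points
- f = 5%: 47.5 - 28.5 = 19.0 points

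Both rules were applied to the same simulated trials. The Stage 1 stop was held fixed, because the SAP Revision C log describes the interim communication as having already happened.

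| Rates | Power, visit-level | Power, subject-level (f = 2% to 5%) | Rules disagree on significance |
|---|---|---|---|
| 50/30 | 0.774 | 0.767 to 0.757 | about 1.7% to 3.1% |
| 45/30 | 0.555 | 0.546 to 0.531 | about 3.1% to 5.5% |
| 30/30 | about 0.017 | about 0.017 | not needed |

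Check at 50/30, f = 5%: 2.42% of trials are significant only under the visit-level rule and 0.74% only under the subject-level rule. The net loss is 2.42 - 0.74 = 1.7 points, and 0.774 - 0.017 = 0.757. If affected subjects respond at half their arm's rate, disagreement falls to about 1.1-2.0% (50/30) and 2.0-3.6% (45/30).

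**6. One subject.** Each reclassified responder moves an arm by 1/125 = 0.8 points. With 38/125 control responders (unstratified test):
- 53/125 on treatment: difference 0.120, pooled rate 91/250 = 0.364, SE = sqrt(0.364 × 0.636 × 2/125) = 0.0609, z = 1.97, one-sided p = 0.0243
- 52/125 on treatment: difference 0.112, pooled rate 90/250 = 0.360, SE = 0.0607, z = 1.84, one-sided p = 0.0325

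**The case against.** **The bullets may only add to the general sentence.** They are introduced as additional rules. Neither steroid bullet uses the word only, as the early-withdrawal bullet does, and neither says that another visit reverts to its observed response. On this reading they set Week 4 and Week 8 status. This is coherent and is the reading to adopt, but the SAP does not state it. The DMARD contrast points the other way, and the Revision C log records a deliberate limit on carrying failure forward for oral steroids, with a half-life rationale. The log is evidence of intent only, and it does not extend that limit to injections.

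**The reach is narrow.** This stands. ACR20 is effectively settled, the general sentence lists EULAR response as an example, and Protocol 17.7 covers the rest. SAP 5.1 says other binary endpoints are analysed like the primary, but that concerns the test.

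**The number is probably small.** This also stands. Such steroid use is prohibited and is a protocol deviation.

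**Safeguards exist.** They are partial.
- SAP 9.2 plans a sensitivity analysis of deviations, for the primary endpoint only and for deviations the sponsor identifies.
- Rescue is tabulated by arm (Table 14.1.2.20) and listed by subject.
- Protocol 12.2.4 makes injected joints unevaluable, which leaves systemic, pain and HAQ-DI effects.
- The rescue sensitivity analysis (8.3.4, extended by 8.5.1) carries forward the pre-rescue value, so it does not compare the two rules.

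**Conclusion.** The contradiction is real and limited. For primary ACR20 and ACR20 from Day 0 it is a programming rule at odds with a settled analysis. For the EULAR, DAS28-CRP MCID and HAQ-DI MCID responses, the SAP text holds both readings and only the Protocol decides clearly.

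The figures are illustrations for primary ACR20. They rest on an assumed 2-5% affected share, equal between arms, with affected subjects responding at their arm's rate. No figure is available for the secondary endpoints, and unequal use between arms could move the result either way.

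A reader might infer more than the documents support:
- **That the primary analysis is undefined, or that the SAP credits these subjects with a response.** Section 8.3.3 and the Protocol say non-response. An observed Week 12 response is implied by the bullets, not stated.
- **That the sample size, stated power or type I error is wrong.** The stated power reproduces. With equal true rates and equal shares affected, rejection is about 0.017 under either rule.
- **That power falls to 0.743 at 50/30 with 5% affected.** That figure lets the rule also change the Stage 1 stop, which is already past.

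**What to change.** Before unblinding, add two statements to SAP 5.8.1:
1. For the Week 12 primary and key secondary binary endpoints, any Protocol-defined rescue before Week 12, including steroid rescue, is non-response, as in Protocol 17.7 and SAP 8.3.3.
2. The visit-level steroid bullets set Week 4 and Week 8 status only.

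Because Revision C limited carry-forward for oral steroids on purpose, report the visit-level Week 12 result as a sensitivity analysis. It could sit with the SAP 9.2 deviation analysis.

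Optionally, say which rule governs the MMRM. Section 5.1 states "The data collected after receiving rescue therapy will be set to missing" while the bullets blank single visits, but this has no confirmatory consequence.

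The cost is two sentences and one sensitivity result, with slightly lower response rates in both arms. Permitted treatment does not change.

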5.8.2 Multiple Assessments and Visits

If a variable (e.g., MRI, TJC, SJC) has been assessed multiple times at the same visit, only the last assessment will be used.

Only completed scheduled visits will be included in summary tables (**Appendix B**). Listings will include scheduled and unscheduled visits (**Appendix C**).

5.9 Data Assurance

All tables, figures and data listings to be included in the report will be independently checked for consistency, integrity and in accordance with the study sponsor's SOPs.

5.10 Consistency Across Study Centers

The consistency of ACR 20 response rate across the study centers will be evaluated using Breslow Day test for homogeneity. Any center with < 5 subjects with ACR20 data in any treatment group will be pooled from largest to smallest until the pooled center has 5 subjects in each treatment group. If heterogeneity is found, exploratory analysis will be conducted to investigate the issue. This may include analysis adjusted for baseline characteristics that significantly differ across sites.

5.11 Coding Dictionaries

AEs will be coded using the Medical Dictionary for Regulatory Activities (MedDRA, version 21.0 or later). Concomitant medications will be coded using the March 2019 or later version of the WHO Drug Global dictionary.

6 SUBJECT DISPOSITION

6.1 Subject Enrollment and Disposition

A summary of subject enrollment will be provided by treatment group for each site. The summary will present the number and percentage of subjects enrolled. For each column, the denominator for the percentage calculation will be the total number of subjects analyzed for that column.

A similar enrollment table will be provided by stratification factor stratum. The denominator for the percentage of subjects in the stratum will be the total number of enrolled subjects. If there are discrepancies in the value used for stratification assignment between the IRT and EDC systems, the value collected in the EDC will be used for the summary.

A listing of subjects with discrepancies in the value used for stratification assignment between the IRT and EDC systems at the time of data finalization will be provided.

The randomization schedule used for the study will be provided in a listing and as an appendix to CSR.

The number and percentage of subjects in whom the implant procedure was attempted and in whom it was successful will be summarized. The primary reason for subject discontinuation will be summarized. Screen failures will be reported in the data listings and the summary table. Data for subject disposition, including termination date and reason, will be listed.

7 DEMOGRAPHICS AND BASELINE CLINICAL CHARACTERISTICS

Demographic data (i.e., age, gender, race, ethnicity) and baseline clinical characteristics (i.e., years since RA diagnosis, treatment history with biologic, targeted synthetic and conventional synthetic DMARDs, baseline clinical variables) will be summarized per treatment group and overall using descriptive statistics for continuous variables and using number and percentage of subjects for categorical variables.

8 EFFICACY ANALYSES

8.1 General Considerations

8.1.1 Missing endpoint data imputation

Below are the descriptions for the imputation methods that may be used throughout the efficacy analyses:

- *Observed case (OC)*. Missing values remain missing. For the categorical composite endpoints, in the case that some components are missing, the composite endpoint assessment will be derived based on the non-missing components. If non-missing components are not sufficient to determine final composite endpoint, then the composite endpoint will be set as missing. For continuous composite endpoints, if any components are missing, the composite endpoints will be set as missing.
- *Last observation carried forward (LOCF)*. Baseline and Day 0 measurements will not be carried forward to post-baseline. Only measurements post Day 0 will be LOCF for continuous and binary response measures. For the composite endpoints, the last non-missing, post-Day 0 observation will be carried forward to subsequent visits for each individual component first, and then the composite endpoints using individual components imputed by LOCF will be calculated as described above. If a subject does not have a non-missing observed record for a post-Day 0 visit, the last post-Day 0 record prior to the missed visit will be used. If the last non-missing observation prior to the missing visits cannot be determined due to multiple

measurements occurring at the same time or the time not available within the same day, the worst outcome will be used for LOCF. If missing components still exist after LOCF, the composite endpoints will be calculated using the same rules as described in OC.

- *Non-responder imputation (NRI)*. For all binary response measurements, starting from OC, all missing will be set as non-responders.

If subject only had baseline measurements, LOCF and OC analyses will not include this subject. But this subject will be treated as non-responder in NRI analyses.

8.2 Clinical Variables

8.2.1 TJC28 and SJC28

The assessment for swelling is the total number of joints with a present swelling and ranges from 0 to 28 for SJC28. The assessment for tenderness is the total number of joints with a present tenderness and ranges from 0 to 28 for TJC28. The following 28 joints will be taken into account for TJC28 and SJC28: shoulder (2 joints), knee (2), elbow (2), wrist (2), fingers (PIP, MCP: 20). All joint assessments will be performed by an independent, blinded joint evaluator. Artificial, ankylosed and missing joints are excluded from swelling and tenderness assessment.

If there are missing observations for tender or swollen joints, then the remaining observations will be assessed and weighted by dividing the number presented by number of non-missing and by multiplying by 28 for the joint count. No imputations for individual joints will be done. If a joint is not evaluable at baseline, then that joint is set to missing throughout the study. If data for more than 50% of the joints are missing at the time of a given assessment, then the total count will be set to missing for that visit.

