12.2.4 TJC28 and SJC28

A total of 28 joints will be scored for presence or absence of tenderness or pain and swelling. All joint assessments will be performed by an independent, blinded Joint Evaluator with appropriate training and experience. Each subject should be assessed by the same Joint Evaluator throughout their participation in the study. The subject's Joint Evaluator *must* be the same at Screening and Week 12. Joints that have been replaced or injected with intra-articular steroids during the study are considered unevaluable.

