6.2 Clinical Variables

For descriptions and definitions of ACR components (TJC28, SJC28, Subject's Pain Assessment, SGA, EGA, HAQ-DI, hsCRP), refer to Section 8.2 of CLP-004.

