6.3 Subgroup Analyses

Response rates for the key exploratory efficacy endpoints, as specified in **Table 2**, will be examined using the following subgroups:

- Number of prior biologic and targeted synthetic DMARDs (e.g., < 4 vs. \geq 4)
- Prior use of JAKi (Yes vs. No)
- RA activity at baseline (DAS28-CRP \leq 5.1 vs. DAS28-CRP $>$ 5.1)

- RA severity at initiation of stimulation (< 4 TJC28 or < 4 SJC28 vs. ≥ 4 TJC28 and ≥ 4 SJC28)
- Augmented therapy (yes, no)

After completion of Week 12 assessments, additional treatment for RA may be provided at any time. The decision about the need, type and timing of treatment is left to the discretion of the Co-PI Rheumatologist and the subject. The initiation of these treatments with study treatment during open-label follow-up is considered “augmented therapy”. Subjects combining stimulation with the following additions to RA therapy will fall into the augmented therapy subgroup for analysis of response rates for key exploratory efficacy endpoints at specific timepoints:

- *Prednisone equivalent >10 mg/day.* If average daily corticosteroid use exceeds 10 mg/day prednisone after a period (time from previous visit up to the day before the current visit), the subject is assigned to the augmented therapy subgroup for that visit.
- *Corticosteroid injection.* If subject received a corticosteroid injection within 30 days prior to a study visit, the subject is assigned to the augmented therapy subgroup for that visit.
- *b/ts/csDMARD.* Subjects who receive treatment with biologic, targeted synthetic, or additional conventional synthetic DMARD, or increased dose of background conventional synthetic DMARD will be assigned to the augmented therapy subgroup for all subsequent visits.

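### A joint that becomes unevaluable after baseline stays in the baseline joint count but drops out of later counts, so percent change compares different joint sets, mainly in the long-term analysis

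*SAP*

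**What the plan says.** Section 8.2.1 of CLP-004 forms each visit's tender and swollen count from the joints available at that visit: "If there are missing observations for tender or swollen joints, then the remaining observations will be assessed and weighted by dividing the number presented by" the number of non-missing joints, with the result multiplied by 28. It adds that "No imputations for individual joints will be done", and it voids the whole count only when more than half the joints are missing.

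The joint set is aligned across visits in one direction: "If a joint is not evaluable at baseline, then that joint is set to missing throughout the study". No rule covers a joint that is evaluable at baseline and not later.

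Protocol 12.2.4 says how that happens: "Joints that have been replaced or injected with intra-articular steroids during the study are considered unevaluable". It sets no end to that status. The SAP's own list is shorter: "Artificial, ankylosed and missing joints are excluded from swelling and tenderness assessment".

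The long-term SAP (CLP-008, section 6.2) has no joint rules of its own. For the ACR components it tells the reader to "refer to Section 8.2 of CLP-004".

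**The concern.** Percent improvement means something only if both visits count the same joints. Here, a joint that was tender or swollen at baseline and is later replaced or injected still counts in the denominator of the change, while the follow-up count is built from the other joints. A count can then appear to fall although no examined joint has changed. Non-responder imputation does not catch this, because a prorated count is not a missing component.

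Both joint counts are mandatory for ACR20/50/70, and both enter DAS28-CRP and CDAI. The 20/50/70% responses in TJC28 and SJC28 are also reported on their own, where a shift in one count is enough. In long-term follow-up, injections are no longer prohibited and response rates are reported without a concurrent sham group.

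**Working it through.** **Inputs**
- Proration over the joints non-missing at each visit; no single-joint imputation; unevaluability carried forward from baseline only (CLP-004, 8.2.1).
- Entry minimum of 4 tender and 4 swollen joints of 28 at consent (Protocol 10.1).
- ACR20 needs at least 20% improvement in both counts plus 3 of 5 other items (CLP-004, 8.3.1).
- Counts below 4 are possible at Day 0, where they define a randomization stratum (Protocol 17.1; CLP-004, 5.5).

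The documents give no worked example of this rule, so there is no stated figure to reproduce.

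**Formula.** Take 28 joints evaluable at baseline, *a* of them active. Suppose *k* of the active joints become unevaluable and every other joint is unchanged.

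Follow-up count = 28(*a* − *k*)/(28 − *k*)

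Scored improvement = 1 − follow-up count/*a* = *k*(28 − *a*)/[*a*(28 − *k*)]

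The true change in the examined joints is 0%.

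**One active joint lost (k = 1)**

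| Reference count | Follow-up count | Scored improvement |
|---|---|---|
| 2 | 1/27 × 28 = 1.04 | 48.1% |
| 3 | 2/27 × 28 = 2.07 | 30.9% |
| 4 | 3/27 × 28 = 3.11 | 22.2% |
| 5 | 4/27 × 28 = 4.15 | 17.0% |
| 8 | 7/27 × 28 = 7.26 | 9.3% |
| 15 | 14/27 × 28 = 14.52 | 3.2% |

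From a count of 1 the scored improvement is 100%. The 20% line is crossed only at a count of 4 or lower.

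**More joints lost.** With two lost, 20% is passed up to a count of 7 (2 × 21/(7 × 26) = 23.1%) but not at 8 (19.2%). With three lost, it is passed up to 10 (3 × 18/(10 × 25) = 21.6%).

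**Inactive joint lost.** The count becomes *a*/27 × 28 = 1.037*a*, a 3.7% worsening at any starting value.

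**Tender-only joint lost, both counts 4.** TJC28 improves by 22.2%, but SJC28 goes from 4 to 4/27 × 28 = 4.15, so the ACR20 joint criteria are not met.

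**Composite scores, both counts 4, joint active on both.** The DAS28-CRP joint terms fall by (0.56 + 0.28) × (√4 − √3.11) = 0.84 × 0.236 = 0.20, against an MCID of 1.2. CDAI falls by 2 × (4 − 3.11) = 1.78, against an MCID of 6 or 12 from moderate or high activity.

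**Role of proration.** Without it, 4 to 3 would score 25%, so proration slightly reduces the artefact. The cause is the unmatched joint set.

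**After the fix.** On the common joint set, a subject with 4 active joints who loses one has 3/27 × 28 = 3.11 at both visits, a 0% change. The same holds for any starting count.

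**The case against.** The strongest reply is that the confirmatory analysis is barely exposed. Protocol 14.4 prohibits intra-articular steroid injection through Week 12. CLP-004 section 5.8.1 sets a visit to failure if an injection fell in the preceding 30 days, and sections 5.8.1 and 8.3.3 make subjects rescued before Week 12 non-responders. That stands. What is left before Week 12 is mainly joint replacement and joints simply not recorded. No difference between arms is shown.

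A reader might infer that one lost joint produces an ACR20 response. It does not. Meeting both joint criteria needs both counts at 4 or lower and a lost joint that was both tender and swollen, and 3 of the 5 other items must still improve.

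A reader might also infer that the error always favours response. It does not: losing a joint inactive at baseline scores as worsening. A joint injected late in follow-up may have flared only after baseline, and the documents do not say how often the affected joint was active at the reference visit.

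Finally, Protocol 12.2.4 and the SAP list can be read together. An injected joint is recorded as unevaluable and reaches the SAP as a missing observation. The SAP list is therefore incomplete rather than contradictory, and nothing in it says that injected joints are to be scored.

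None of this supplies the missing rule for a joint lost after the reference visit.

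**Conclusion.** The gap is real: followed as written, section 8.2.1 gives a wrong percent change whenever a joint is lost after the reference visit. The size per subject is that tabulated above, assuming 28 joints evaluable at the reference visit and no change in the others. From a count of 4, the 20% line is still reached if at least 16 joints were evaluable.

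The main exposure is CLP-008. There injections are permitted, and reference counts can be below 4, because change is taken from Day 0 for subjects randomized to treatment and from Week 12 for crossed-over controls. Joint-count responses are reported in their own right. The analyses are exploratory, so what is at stake is the accuracy of descriptive response rates. Within the Week 12 analyses, the key secondary ACR20 from Day 0 can also start from counts below 4, but only through the routes that remain open there.

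CLP-008 section 6.3 places an injected subject in the augmented subgroup for a visit "If subject received a corticosteroid injection within 30 days prior to a study visit", whereas the joint stays unevaluable afterwards. With visits 84 days apart and injections spread evenly (an assumption), (84 − 30)/84 = 64% of injections would go unflagged. A reader might take this as the bias in the subgroup without augmented therapy, but it is not. It is a share of an unknown number of injections. It ignores subjects already in the augmented subgroup for all later visits because of a DMARD change, and it includes injections into joints outside the 28 or inactive at the reference visit.

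The documents give no frequency of lost joints, so no effect on any response rate can be computed. This is a cheap improvement to make, not a threat to the primary result.

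**What to change.** In CLP-004 section 8.2.1, and so in CLP-008 section 6.2, state that for percent change, response, and DAS28-CRP and CDAI change, a joint that becomes unevaluable after the reference visit is removed from both the reference and the follow-up count, with both prorated on the joints evaluable at both visits. The reference visit is consent, Day 0 or Week 12, as the endpoint requires. Add steroid-injected joints to the SAP exclusion list so that it matches Protocol 12.2.4.

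The cost is about two sentences and a small programming change; Protocol 12.2.4 already has each of the 28 joints scored. The reference count of an affected subject can then differ from visit to visit, which the tables should footnote. Response rates may become slightly less favourable. The rule removes spurious worsening as well as spurious improvement.
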